### 15.2.1 Laboratory parameters

Continuous and categorical laboratory parameters will be analyzed as described in Section 15.2 with individual specifications outlined in Table 2. The display of continuous laboratory parameters

will be by parameter group (clinical chemistry, clotting, hematology, and urinalysis). Categorical urinalysis parameters will be additionally classified as normal or abnormal.

Central laboratory parameters will be analyzed as described in the following paragraphs. No statistical analysis of local laboratory assessments, pregnancy tests, and drugs of abuse tests will be done. In general, all central laboratory parameters will be reported using Système International d'Unités (SI) units. Selected parameters will additionally be reported using US conventional units to facilitate safety data review (Section 19.4). The corresponding analyses of these parameters will be repeated using values in US conventional units.

Subjects potentially qualifying for Hy's law criteria (FDA 2009), i.e., subjects showing post-baseline abnormal hepatic values, will be presented in a separate listing. Subjects fulfilling the following 2 criteria potentially qualify for Hy's law:

- ALT > 3x ULN or AST >3x ULN.
- Total bilirubin > 2x ULN.

Table 2: Analysis of laboratory parameters

Parameter group	Parameter	Table of descriptive statistics	Frequency table (low/high)	Shift table	Mean plot	Shift plot
Clinical chemistry parameters (continuous)	Albumin	X	X	X		
	Alkaline phosphatase	X	X	X	X	X
	ALT	X	X	X		
	AST	X	X	X		
	Bilirubin	X	X	X		
	Calcium (albumin-corrected)	X	X	X	X	X
	Creatine phosphokinase	X	X	X		
	Creatinine	X	X	X	X	X
	Estimated GFR	X	X	X		
	GGT	X	X	X		
	Glucose	X	X	X		
	LDH	X	X	X		
	Magnesium	X	X	X		
	Parathyroid hormone	X	X	X		
	Phosphate	X	X	X		
	Potassium	X	X	X		
Protein	X	X	X			

Parameter group	Parameter	Table of descriptive statistics	Frequency table (low/high)	Shift table	Mean plot	Shift plot
	Sodium	X	X	X		
	Tricylglycerol lipase	X	X	X		
	Urea	X	X	X		
	Uric acid	X	X	X		
	Vitamin D	X	X	X		
Hematology parameters (continuous)	Hematocrit	X	X	X		
	Hemoglobin	X	X	X		
	Platelet count	X	X	X		
	RBC	X	X	X		
	WBC	X	X	X		
Urinalysis parameters (continuous)	pH	X	X	X		
	Albumin (microalbumin)	X	X	X		
	Creatinine	X	X	X		
	Urinary albumin/creatinine ratio (semi-quantitative dipstick)	X	X	X		
	Calculated urinary albumin/creatinine ratio (central laboratory)	X	X	X		
Urinalysis parameters (categorical)	Bilirubin	X		X		
	Blood	X		X		
	Glucose	X		X		
	Ketone	X		X		
	Leukocytes	X		X		
	Nitrite	X		X		
	Protein	X		X		
	Urobilinogen	X		X		

ALT = alanine transaminase; AST = aspartate transaminase; GGT = gamma-glutamyltransferase; INR = international normalized ratio; LDH = lactate dehydrogenase; MCH = mean corpuscular hemoglobin; MCHC = mean corpuscular hemoglobin concentration; MCV = mean corpuscular value; RBC = red blood cell; WBC = white blood cell.

Graphical presentations over time and respective shift plots will be done for the following continuous laboratory parameters:

- Alkaline phosphatase.

- Calcium (measured).
- Creatinine (serum).
- Estimated glomerular filtration rate (eGFR).
- Quantitative urinary albumin/creatinine (central laboratory value).

Urine samples potentially obtained from women of child-bearing potential will be tested locally using a urine  $\beta$ -human chorionic gonadotropin ( $\beta$ -HCG) pregnancy dipstick test. The results will be presented in a subject data listing.

Urine samples will be obtained from all subjects at the Enrollment Visit for testing for drugs of abuse. The drugs to be screened for using suitable validated methods (e.g., dipstick) include: cocaine, 3,4-methylenedioxy methamphetamine, ecstasy (MDMA), amphetamines, cannabinoids. The results will be presented in a subject data listing.

### **15.2.2 Vital signs**

Descriptive statistics for the vital signs parameters (systolic and diastolic blood pressure, pulse rate, weight, body mass index BMI [kg/m^2]) will be analyzed as described in Section 15.2.

Frequency tables and shift tables with respect to sponsor-defined alert ranges as described in Section 15.2 will be created.

### **15.2.3 Electrocardiogram**

Descriptive statistics for the electrocardiogram (ECG) parameters (continuous) heart rate, PR interval, QT interval, QTcF interval, RR interval will be analyzed as described in Section 15.2.

The ECG printouts will be interpreted by the investigator as “normal”, “abnormal, but clinically not relevant”, or “abnormal and clinically relevant”. Results from this interpretation will be reported in subject data listings. Moreover, the results from the ECG interpretation will be descriptively summarized.

In addition, a subject data listing of all abnormal, clinically relevant findings as documented by the investigator in the e-CRF will be created.

## **15.3 Physical examination**

A general physical examination will be done at the Enrollment Visit (Visit 1) by rating each body system as *normal* or *abnormal*. At all subsequent visits, including unscheduled visits, updates of the physical status since the previous visit are recorded by rating the body system as *unchanged* or *changed*.

The results will be presented in a subject data listing.

## **16 INTERIM ANALYSIS**

### **16.1 Interim analysis of efficacy**

The interim analysis will be further described in a separate SAP as it will be performed on the pooled data of two trials.

---

## **18 CHANGES TO THE SAP**

### **18.1 Amendments**

Not applicable.

## **19 APPENDIX**

### **19.1 Data derivation and analysis rules**

The purpose of this section is to give technical details for the implementation of the SAP.

#### **19.1.1 General specifications**

##### **19.1.1.1 Percentages and decimal places**

If not otherwise specified, the following rules are applied:

- Percentages are presented to 1 decimal point.
- Percentages equal to 0 or 100 are presented as such without a decimal point.
- For descriptive summary statistics, the same number of decimal places as in the raw data are presented when reporting minimum and maximum values, 1 more decimal place when reporting mean, median, quartiles and confidence interval and standard deviation.
- P-values are presented to 3 decimal points. P-values <0.001 will be reported as such.
- Ratios are presented to 3 decimal points.

The above described displaying rules must not be changed (e.g., rounding) for the integrated clinical trial report text and are used 1:1 in the body report as well. For analysis of pharmacokinetic data, see also Section 19.1.5.

#### 19.1.1.2 Presentation of descriptive statistics

Calculation of mean: if not otherwise specified (e.g., for pharmacokinetic data), the arithmetic mean is used.

Table 3: Presentation of descriptive statistics in clinical trials

Number of non-missing values	n	Missing n	Mean	SD	Min	Q1	Median	Q3	Max
0	+	+	-	-	-	-	-	-	-
1.2.3.4	+	+	+	-	+	-	+	-	+
≥5	+	+	+	+	+	+	+	+	+

+ summary statistic will be presented; - summary statistic will not be presented.

CI = confidence interval, Max = maximum, Min = minimum, n = number of values, Q1 = first quartile, Q3 = third quartile, SD = standard deviation

#### 19.1.1.3 Presentation of differences and changes

For differences between active comparator and placebo, the active comparator will constitute the minuend and placebo the subtrahend.

For changes from baseline, the baseline value will constitute the subtrahend and the later value the minuend.

#### 19.1.1.4 Trial day count

The day of baseline visit (Visit 2) is defined as trial Day 1.

Calculate the trial day according to the following rules:

- If date < trial Day 1, then trial day = Date – trial Day 1.
- If date ≥ trial Day 1, then trial day = Date – trial Day 1 +1.

#### 19.1.1.5 Presentation of units

If applicable, parameters will be displayed together with the used unit of measurement. The unit of measurement is enclosed in square brackets ([ ]).

#### 19.1.1.6 Presentation of dates

Where applicable (e.g., in listings), dates will be displayed in ISO8601 format (example: 2014-09-29T12:16, see CDISC 2013). In case of incomplete dates, both the original value and the imputed value is displayed.

#### 19.1.1.7 Handling of missing values

At each time point/visit, all subjects still in the trial are reported. This is defined as all subjects that have not discontinued the trial before the respective visit and are identified by a visit date. Missing values will be taken into account as missing in the analysis. The number of observed values and the

number of missing values must add up to the number of subjects in the trial at the respective time point/visit.

Unless otherwise specified in the SAP, missing values will not be imputed. If missing values are imputed, the result of all imputation strategies and newly derived information must be stored in the ADaM data set. The shifts required for the shift tables should already be included in the ADaM data set.

Imputed values will be listed in the subject data listing and marked as imputed.

#### **19.1.1.8 Visit windows**

Since all assessments not done in the eDiary assessments are linked to specific visits no visit windows definition is needed. Nevertheless if values or changes from baseline to a specific week are to be displayed the respective visit value is to be used. E.g. for responder analysis based on the tablet computer described in Section 13.2.2 the average pain intensity Week 26 is needed, which in fact related to the value documented for Visit 11.

#### **19.1.1.9 Handling of data from early termination visits**

Subjects who discontinue the 52-week trial period before their Week 52 visit (Visit 17) are requested to undergo an Early Termination Visit with identical procedures to Visit 17. Data from the Early Termination Visit recorded under Visit 17 will not be included in the analysis of data from scheduled visits at Visit 17.

Instead data from the Early Termination Visit will be assigned to the nearest scheduled visit based on the study day of the early termination visit and the planned visit day. The planned visit day is

- Day 1 for Visit 2
- Day 4 for Visit 3
- Day 7 for Visit 4
- Day 10 for Visit 5
- Day 15 for Visit 6
- Day 43 for Visit 7
- Day 85 for Visit 8
- Day 113 for Visit 9
- Day 155 for Visit 10
- Day 183 for Visit 11
- Day 186 for Visit 12 (only if subject is retreated)
- Day 189 for Visit 13 (only if subject is retreated)
- Day 192 for Visit 14 (only if subject is retreated)
- Day 197 for Visit 15 (only if subject is retreated)
- Day 253 for Visit 16
- Day 365 for Visit 17

In case of equal distance to two scheduled visits the earlier visit will be chosen. If the assigned visit already occurred before the early termination visit, then the data will be assigned to the next

scheduled visit. Visits 12, 13, 14 and 15 are only applicable for subjects who have been treated in Treatment Period B.

Data from the Early Termination Visit will be analyzed using the re-assigned visits.

#### **19.1.1.10 Assessments of on-treatment-period**

For the calculation of the on-treatment-period the date information given for IMP administration will be used as documented in the e-CRF and according to the definition in Section 8.2.2.

#### **19.1.1.11 Conversion of time intervals**

If a time interval was calculated in minutes, hours or days and needs to be converted into months or years, the following conversion factors will be used:

- 1 month = 30 days.
- 1 year = 365.25 days.

#### **19.1.1.12 End of treatment**

End of treatment is the date of last administration of IMP given on the End-of-trial page in e-CRF.

#### **19.1.1.13 Mandatory tables without data**

Recommended tables must be created. If no subject qualifies for the table, the header will be created and the table itself will be replaced by “No subject in this category”.

#### **19.1.1.14 Kaplan-Meier analysis**

For Kaplan-Meier analyses in the 12-week trial period, the unit of time is days, the start time is the date/time of first IMP, and the censoring time is the day of Visit 8 or, in case of dropouts, the day of the Early discontinuation Visit 17.

### **19.1.2 Disposition**

There are no trial-specific definitions for this trial.

#### **19.1.2.1 Subject discontinuation**

Reasons for subject discontinuation as specified in the End-of-trial page or reason for permanent discontinuation of IMP from the respective Treatment Period A/B completer page of the e-CRF will be used.

#### **19.1.2.2 Protocol deviations**

Protocol deviations are based on the analysis dataset ADDV. Major protocol deviations are retrieved from the respective SDTM dataset (SDTM.DV.DVCAT). No further protocol deviations are programmed in the analysis datasets for ADDV (if not otherwise specified in the SAP).

### **19.1.3 Demographics and other baseline characteristics**

#### **19.1.3.1 Subject demographics**

##### **Derivation of age**

Age as derived in SDTM.DM.AGE will be used

**Derivation of BMI:**

BMI is extracted from the SDTM.

**Derivation of race:**

If for race more than 1 entry per subject is documented, a category “multiple” will be created.

**19.1.3.2 CRPS history**

For CRPS history, time since inciting or precipitating event (months), time since onset of CRPS symptoms (months), time since diagnosis of CRPS (months) are derived.

If the corresponding date reported in the eCRF is incomplete, e.g., missing day or month (year is mandatory), then the missing day or month will be imputed. Missing dates will be imputed conservatively, i.e., missing values will be imputed in such a way that the imputed date leads the longest possible time since event. Missing months will be imputed by the first calendar month of the year, and missing days will be imputed by the first calendar day of the (imputed) month.

Missing date	Imputed date
2018-Mar	2018-Mar-01
2018	2018-Jan-01

**19.1.3.3 Prior and concomitant medication or therapy**

Prior and concomitant medication is collected as of enrollment in the e-CRF and described like that in the trial protocol. For the analysis, the definition as described in the following is used.

The following rules are used to define the categories “prior” and “concomitant” medication.

Pre-requisite is a complete date of first dose of IMP (entered or imputed).

Stop of medication Date	Condition	Category
Complete date is available	Stop date is earlier than date of first dose of IMP.	Prior
Missing month	Year of stop date is earlier than year of first dose of IMP.	Prior
Missing day	Month/year of stop date are earlier than month/year of first dose of IMP.	Prior
Otherwise		Concomitant

Medication ticked in the e-CRF as “continuing” will be classified as concomitant.

For time to first concomitant analgesic medication start dates might need to be imputed. Imputation will be done as for CRPS history but if imputed date would be before first IMP date of first IMP will be used.

**19.1.4 Efficacy analysis**

Not applicable.

### **19.1.5 Analysis of pharmacokinetic and pharmacodynamic parameters**

Pharmacokinetic values (concentrations and concentration related parameters) including their descriptive statistics will be shown using 3 significant digits e.g., 123 or 12.3 or 0.123. Values above 1000 will be presented as integers. Statistical calculations will be performed with values that have not been rounded.

The coefficient of variation (CV) will be presented as percentage with 1 decimal.

A missing pre-dose value in single-dose trials will be replaced by 0.

The time axis of the plots should be broken after the first day and before the last one using different scales for the different kind of profiles (e.g., the 0-24 h time period on the first and the last day should have approximately the same width as the remaining part with the trough values).

#### **Derivation of geometric mean and geometric coefficient of variation**

Geometric mean =  $\exp(\text{arithmetic mean of log-transformed values})$

Zeros will be excluded from the calculation of the geometric mean.

Geometric. CV% =  $(\text{sqrt}(\exp(\text{variance for log transformed data}) - 1)) * 100$

### **19.1.6 Safety analysis**

#### **19.1.6.1 Adverse events**

The result of all imputation strategies (e.g., incomplete start dates of adverse events), combination of observations and new derived information (e.g., treatment-emergent flag) must be stored in ADaM data set.

[figure not shown]
#### **Handling of missing date information**

The term missing date/time refers to a completely missing date /time or to an incomplete date/time where parts are not available e.g., missing hours.

The following imputation strategy is applied.

If the number of adverse events with missing date/time information exceeds 10%, the imputation strategy is only applied to assess if an adverse event is a TEAE but not for any other calculation (e.g., duration, onset).

Missing start and end date/times will be imputed conservatively, i.e., missing values will be imputed in such a way that the duration of the adverse event is considered with the longest possible duration and such that, whenever the adverse event may potentially start after first IMP administration, the adverse event will be handled as a TEAE.

I1-I4: imputation steps

C1-C4: checkpoints

AE = adverse event, IMP = investigational medicinal product

Figure 1: Graphical overview about the imputation strategy

Further explanations on the flow chart:

The different steps of the displayed imputation strategy must be completed from the first to the last step. All procedures in each step must be completed in the order given.

- Imputation:
  - I1: Impute with date/time of first IMP  
{If administration of IMP was not collected with time information set adverse event start time to 00:00.}
  - I2:
    - a) Impute with first calendar day and/or first calendar month  
Imputation will be done based on the available partial information starting with month and then day. The respective first month and day will be chosen for imputation:

Missing date	Imputed date
2014-Mar	2014-Mar-01
2014	2014-Jan-01

- b) Impute with first hour and/or first minute  
Imputation will be done based on the available partial information starting with hour and then minutes. The respective first hour of a day and first minute will be chosen for imputation. “00:00” will be considered as the first hour/first minute per day.

Missing time	Imputed time
11:--	11:00
--:--	00:00

}

- I3: Impute with date/time of informed consent signed  
If signing of informed consent was not collected with time information, set the adverse event start time to 00:00.
- I4:
  - a) Impute with last calendar day and/or calendar last month  
Imputation will be done based on the available partial information starting with month and then day. The respective last month and day will be chosen for imputation:

Missing date	Imputed data
2014-Mar	2014-Mar-31
2014	2014-Dec-31

For February leap years must to be taken into account when calculating the last day in February.

- 1.1. b) Impute with last hour and/or last minute  
Imputation will be done based on the available partial information starting with hour and then minutes. The respective last hour of a day and last minute will be chosen for imputation. “23:59” will be considered as the last hour/last minute per day.

Missing time	Imputed time
11:--	11:59
--:--	23:59

- Checkpoints
  - C1: The decision must be taken based on the available information (date /time) before imputation.
  - C2: Adverse event stop date before first IMP
- 1.2. 1) The decision must be taken based on the available information (date/time) before imputation.
  - 2) If the end date is completely missing (with or without the information that the adverse event was continuing), this will be considered as after first IMP.
  - 3) If no IMP was given, this will be treated as adverse event stop date before the first IMP.
  - C3: The decision must be taken based on the available information (date/time) before imputation.
  - C4: The decision must be taken based on the available information (date/time) before imputation.

A replacement of missing year for adverse event start information is not foreseen. If needed, this will be considered on a case-by-case decision which must be documented together with the documentation of ADaM data sets.

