### **Assignment adverse events to time periods/trial phases**

Assignment of adverse events to time periods/trial phases will be done after replacement of missing date/time information.

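### Adverse events dated only to the month or year of Visit 11 are imputed to before the first Period B infusion, so events that followed it are counted in Follow-up Period 1, under Placebo for placebo starters

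*SAP*

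**What the plan says.** In SAP 19.1.6.1 (Handling of missing date information) an incomplete start can be filled in three ways:

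- "I1: Impute with date/time of first IMP". This is the only step tied to dosing.
- Step I2: "Impute with first calendar day and/or first calendar month", explained as "The respective first month and day will be chosen for imputation". For times, "The respective first hour of a day and first minute will be chosen for imputation", with midnight as the first value.
- "I3: Impute with date/time of informed consent signed".

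Step I4 uses the last calendar or clock value. Because the section aims for the longest possible event duration, I read I4 as the stop-date step. Checkpoint C2 asks about "Adverse event stop date before first IMP", so it too looks only at the first IMP. The safeguard the section states is that "whenever the adverse event may potentially start after first IMP administration, the adverse event will be handled as a TEAE".

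A later paragraph of 19.1.6.1 adds: "Assignment of adverse events to time periods/trial phases will be done after replacement of missing date/time information". SAP 15.1 displays TEAEs in two phases, Treatment Period A/Follow-up Period 1 and Treatment Period B/Follow-up Period 2, and links them to treatment by start date. It gives no date or time at which one phase ends and the next begins. Under SAP 8.1 the groups up to Week 26 are Placebo and Neridronic acid 400 mg. Finally, if more than 10% of adverse events have missing date/time information, 19.1.6.1 limits imputation to deciding TEAE status.

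**The concern.** For placebo starters who enter Period B, Visit 11 is the first exposure to neridronic acid. Protocol 8.2 says acute phase symptoms typically follow the first administration, and Protocol 1.4.2 requires acetaminophen around the first infusion of Period B as well as Period A. At Visit 2 the SAP resolves doubt about timing by counting the event as treatment emergent. At Visit 11 the same steps resolve doubt the other way, toward the time before the infusion.

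What is at stake is attribution in the by-phase safety tables. A misplaced event in a placebo starter leaves the Placebo + Treatment Period B column, and the combined neridronic acid group that SAP 15.1 adds for that phase, and joins the double-blind Placebo column.

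There is also a gap in the rules. Phase assignment relies on imputed dates, but above the 10% threshold those dates may be used only for TEAE status, so no phase rule is left.

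**Working it through.** **1. Reproducing the SAP's examples.** Coding I2 as written returns the SAP's four worked results: 2014-Mar becomes 2014-Mar-01; 2014 becomes 2014-Jan-01; 11:-- becomes 11:00; a fully missing time becomes 00:00.

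**2. One case.** A placebo starter has the first Period B infusion on 2019-07-18 at 09:00 and an event on 2019-07-19, recorded as 2019-Jul. The first IMP was 182 days earlier (2019-01-17), so I1 does not apply. I2 gives 2019-07-01, before the infusion. The event goes to Follow-up Period 1, under Placebo.

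**3. All Visit 11 dates.** Assumptions: infusion at 09:00; first IMP 182 days before; Visit 11 equally likely on each of 1,461 days (four years, 48 months). Because the SAP states no cut, two are tried: the date/time of the first Period B infusion, and its calendar date only.

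Let k be the number of calendar days from Visit 11 to true onset (k = 0, 1, 3, 10 for onset 6 h, 24 h, 72 h and 10 days after infusion).

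- *Month-only record.* The event is placed correctly when onset falls in the next month, which happens on 48k Visit 11 dates. A date-only cut also rescues the 48 dates when Visit 11 is on the 1st. Share misplaced: (1461 − 48k)/1461 under a date/time cut; (1461 − 48(k + 1))/1461 under a date-only cut.
- *Year-only record.* Same argument with 4 in place of 48. If the first IMP was in the same year, I1 applies instead, and that date also precedes Visit 11.

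| Recorded to | True onset | Date/time cut | Date-only cut |
|---|---|---|---|
| Month | 6 h | 1461/1461 = 100% | 1413/1461 = 96.7% |
| Month | 24 h | 1413/1461 = 96.7% | 1365/1461 = 93.4% |
| Month | 72 h | 1317/1461 = 90.1% | 1269/1461 = 86.9% |
| Month | 10 days | 981/1461 = 67.1% | 933/1461 = 63.9% |
| Year | 6 h | 1461/1461 = 100% | 1457/1461 = 99.7% |
| Year | 10 days | 1421/1461 = 97.3% | 1417/1461 = 97.0% |
| Day, no time | 6 h (Visit 11 date) | 100% | 0% |
| Day, no time | 24 h or later | 0% | 0% |

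These are shares of post-infusion events with that kind of incomplete record, not of all events. Month-only dates in a month after Visit 11 are placed correctly.

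**4. With a second anchor.** If a partial start compatible with onset at or after the first Period B infusion is assigned to Period B, the share misplaced falls to 0% in every scenario. The cost is that true pre-infusion events with the same partial date move into Period B.

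**The case against.** The strongest reply is that this will seldom happen. Protocol 12.4.1 asks for start date and time, and adverse events are recorded before and after the infusion at Visit 11 and again at Visits 12 to 15, so month-only dates there should be uncommon. That stands, and it limits the size.

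Second, the effect is visible and descriptive. SAP 19.1.1.6 and 19.1.1.7 show original dates beside imputed ones and mark imputed values in listings, and SAP 15 plans no safety tests. This also stands, but listings do not correct the summary tables.

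Third, the dedicated acute-phase summary (SAP 15.1.2) counts the symptom terms only within 3 days of the 1st IMP. If that means Visit 2, Period B symptoms are outside it whatever their phase, so the exposure is mainly in the general by-phase tables.

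Fourth, Figure 1 was not legible in the copy available, and C1, C3 and C4 appear without their conditions. The result does not depend on them: the text lists every value a start can take, and for a month-only or year-only record covering Visit 11 none falls later than the start of the Visit 11 day.

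Three stronger readings are tempting but not supported:

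- *That the midnight rule in itself misplaces infusion-day events.* It does so only for untimed events on the Visit 11 date, and only under a date/time cut. SAP 15.1 states no cut, and its wording on treatment assignment refers to start date.
- *That the rule always favours the drug.* Neridronic acid starters re-treated in Period B have their misplaced events added to the neridronic acid column of the controlled phase.
- *That the number of affected subjects can be stated.* Assuming 45 to 72 placebo starters enter Period B, 10% to 30% have an infusion-day event and 10% to 30% of those lack a time, the range is 45 × 0.10 × 0.10 = 0.45 to 72 × 0.30 × 0.30 = 6.5. Every input is assumed, the count covers only untimed infusion-day events, and under a date-only cut it is zero. A missing-time rate above 10%, if general, would also trigger the restriction on imputation; at 10% the upper figure is 72 × 0.30 × 0.10 = 2.2.

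**Conclusion.** The point holds for starts recorded only to the month or year of Visit 11. As written, the rules put such events in Treatment Period A/Follow-up Period 1 even when they followed the first Period B infusion; the exception is a Visit 11 on the first day of that month or year, which helps only under a date-only cut. For placebo starters this counts a possible neridronic acid event under Placebo. For neridronic acid starters it changes the phase but not the drug. For untimed events on the Visit 11 date, the answer depends on a cut the SAP does not give.

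Given such a record, misplacement is close to certain for onsets within three days of the infusion. The number of records cannot be derived from the documents and is probably small. TEAE status is safe, because the on-treatment period in SAP 8.2.2 runs without a break from the first IMP, and total counts do not change. This is a stated rule that gives a wrong attribution, so it merits correction despite its modest size.

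**What to change.** In SAP 19.1.6.1, with a cross-reference in 15.1:

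1. Define the boundary between the two displayed phases as the date/time of the first Period B infusion.
2. For subjects treated in Period B, assign an incompletely dated event to Treatment Period B/Follow-up Period 2 unless the available information, including the stop date, excludes onset at or after that infusion. Do this with a phase-assignment flag only. Overwriting the imputed start would shorten event durations, against the section's longest-duration aim.
3. State that this phase rule also applies when more than 10% of adverse events have missing date/time information.

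Items 1 and 2 belong together: the date/time cut alone would misplace every untimed post-infusion event on the Visit 11 date. The cost is one added SAP rule and one derived flag in ADaM. The downside is that a few true pre-infusion events will be counted in Period B, the same trade-off the SAP already accepts at Visit 2.
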